## RESEARCH DESIGN AND METHODS

### Conceptual Model

Based on our work with Veterans with chronic pain, coupled with studies demonstrating effectiveness of peer support in other chronic conditions, the next step in our research is to explore the effectiveness of placing a peer coach in a role similar to that of the nurse care manager. Although a peer coach does not have a nurse’s clinical training, the coach has successfully adopted self-management strategies, and shares many of the same experiences as other Veterans with pain. This unique position potentially places a Veteran peer coach in a stronger position to deliver motivation, support, and accountability—characteristics that Veterans in our prior studies tout as critical to effective self-management. Examining peer coaching for Veterans with chronic pain is a logical next step based on our prior research, and research in other conditions suggests a peer coaching model may be an effective intervention for Veterans with chronic pain, with high potential for implementation across VA.

### Overview of Study Design

We will conduct a 2-arm randomized controlled trial with Veterans who have chronic musculoskeletal pain. The trial will compare a 6-month peer coaching self-management intervention with a control group consisting of a 2-hour class on pain and pain self-management. We will compare changes in pain between the two groups (Aim 1) and examine secondary outcomes: self-efficacy, pain coping, patient activation, social support, health-related quality of life, and health service utilization (Aim 2). The 2-arm design will allow for direct comparison between Veterans receiving information on self-management (control), versus receiving self-management information combined with the motivation and support delivered by a peer coach and described in our conceptual model.

In addition to testing the effectiveness of the intervention, we will assess facilitators and barriers to implementation through qualitative interviews with study participants (peer coaches and Veterans from the intervention arm) and PACT staff, where a peer support program would most likely be implemented. The study duration will be 4 years, to allow for peer coach and Veteran recruitment, peer coach training, completion of the 6-month intervention, assessment of outcomes at 6 and 9 months, and the pre-implementation interviews.

### **Study Sites**

Roudebush VAMC (RVAMC) is an urban, university-affiliated tertiary care center which provides health care for more than 50,000 veterans and houses five primary care clinics. An RVAMC expansion clinic, Indy West Clinic, opened in 2010 and will also serve as a study site. RVAMC is the parent facility of three Community-Based Outpatient Clinics (CBOCS), in Terre Haute, Martinsville, and Bloomington, IN. These 9 clinics, which staff 75 primary care providers, will serve as study sites.

### **Recruitment and Training of Peer Coaches**

Recruitment: We have three primary sources for recruiting peer coaches: 1) Veterans who served as peer coaches in IMPPRESS (7 out of 9 expressed interest in serving as a coach again); 2) Veterans who completed the intervention arm of one of our previous chronic pain studies involving pain self-management instruction (ESCAPE, PI: [name]; CAMEO, PI: [name]; SCOPE, PI: [name]). In these studies completers were asked for permission to be contacted for future studies. We successfully recruited 10 peer coaches for IMPPRESS in one month using this approach. From these two completed and one ongoing study we have a pool of approximately 250 potential peer coaches. 3) Veterans with chronic pain (see ICD-9 codes in Section D2c) who are recommended by their PCPs. Although we did not need this strategy in IMPPRESS because of successful recruitment of participants from prior studies, one of our co-investigators, [name], has successfully used this method for peer studies of Veterans with diabetes.

Manual: Each peer coach will be given a manual to refer to and serve as a guide during the intervention. The Peer Coach Manual consists of two parts: 1) Self-Management Knowledge (this portion is identical to the Veteran manual), and 2) How to be a Peer Coach. See Table 1. This manual was developed and refined in IMPPRESS, drawing on the study manual from [name] ESCAPE trial (Part 1), and on the Peer Specialist Manual used by VHA's Office of Mental Health Services (Part 2, shared by [name], Director of VA Peer Support Services, see letter of support). In addition, during IMPPRESS, our study psychologist, [name], developed a section on motivational strategies, grounded in the motivational interviewing literature. The peer coach manual is in Appendix 1.

Training: Three to 4 coach training sessions will be scheduled as coaches are recruited. Once 10 coaches are recruited, a training session will be scheduled, and coaches will be assigned Veterans. This process will continue until all peer coaches are recruited, trained, and matched with Veterans.

Peer coach training will consist of one 3-hour session taught by [name]. [name] has trained peer coaches for IMPPRESS and has delivered self-management instruction to Veterans with chronic pain in several prior studies conducted by Drs. [name] and [name]. Each training session will be audio recorded to ensure quality and consistency. Training will emphasize the elements of self-management and support highlighted in the conceptual model (Section D1): 1) self-management strategies/exercises, 2) making adjustments in strategies to find what works, 3) setting and providing accountability to goals, 4) motivating/supporting. Training will be didactic and participative. Particular focus will be on teaching and role-playing to help peer coaches work with their assigned Veterans to accomplish the four intervention

elements listed above. The direct-observation fidelity checklist will be used as a training tool during role-playing.

Part 1: Self-Management Knowledge	Part 2. "How to be a Peer Coach"
Chronic Pain Basics	What is a Peer?
-Biopsychosocial Model	Cultural Competence
-Gate Control Theory of Pain	Communication Skills
Relaxation Skills	Managing Crisis and Emergency Situations  Motivational Strategies
Activity Pacing	
Cognitive Behavioral Skills	
Self-Care Skills	
Interpersonal Skills	

Peer Coach

Supervision: [name] will be available on an ongoing basis for consultation with questions or problems. In addition, she will conduct 1) individual "check-in" calls with peer coaches, and 2) regular group supervision ("booster") sessions with peer coaches via conference call. "Check-in" calls will be with individual peer coaches primarily at the beginning of the intervention period to ensure that coaches

are successfully making initial contact with their assigned Veterans, to help facilitate this contact when needed, and provide any other individual help or guidance needed. [name] will also make individual calls throughout the intervention as needed. All calls will be logged (date/time, peer coach, brief summary, length of call, any other relevant information).

Group supervision ("booster") telephone sessions will be conducted by [name] every 2 weeks for the first 2 months of the intervention period, after which time they will occur monthly. (Frequency of meetings can be adjusted if needed.) This was the schedule followed in IMPPRESS. These "booster" supervision sessions are relatively informal, involving discussion among peer coaches on how their calls/meetings with Veterans are going and providing follow-up tips on communication strategies and reinforcement. Many peer coaches in IMPPRESS found these booster sessions to be more helpful than the initial training, since they were able to discuss practical situations and problems as they arose. Booster sessions serve several key functions: 1) "Getting things going" at the beginning of the intervention when peer coaches and Veterans are making initial contact; 2) Reminding peer coaches to contact their Veterans regularly; 3) Troubleshooting issues or questions; 4) Providing additional training on the use of motivational strategies to address any difficulties with Veterans' goal attainment; 5) Providing motivation, encouragement, and reinforcement of their roles as peer coaches; and 6) Serving as a tool to check and maintain intervention fidelity. An added benefit of these regular calls in IMPPRESS was the peer coaches developed a sense of camaraderie and community among themselves as they shared stories of their experiences in the study. This culminated with a pizza party for the coaches at the end of the intervention period. Because these sessions involve multiple study participants, coaches are instructed not to use participant names when talking about their assigned partners, to protect participants' private health information. [name] will keep detailed field notes documenting the content and duration of these calls, as we did in IMPPRESS.

**Recruitment of Veterans**

Our Center's Data Management Group will run a query in CPRS (Computerized Patient Record System) to identify potentially eligible patients, who will be recruited from 9 clinics: Roudebush VAMC's 5 primary care clinics, the Indy West Clinic, and the 3 Community-Based Outpatient Clinics (CBOCs) at Bloomington, Martinsville, and Terre Haute. Veterans with musculoskeletal pain (ICD-9 codes 715, 719, 721, 722, 723, 724, 726, 729.0, 729.1, 729.3, 729.5, 738.4, 738.5) will be identified. Primary care providers (PCPs) will be contacted to gain permission to recruit their patients. We have successfully used this recruitment method in

several past studies, with over 90% of PCPs agreeing to allow access to their patients. For IMPPRESS, we successfully recruited 20 patients in 6 weeks using this method, after needing permission from only 2 PCPs to achieve our recruitment goal. Based on this experience, we anticipate little difficulty recruiting from multiple PCPs' panels across 9 clinics.

**Inclusion/Exclusion Criteria:** Once potentially eligible Veterans are identified and PCPs have granted permission to recruit, we will contact Veterans to identify those who meet study inclusion/exclusion criteria. Potential participants will be told that we are conducting a study to learn how Veterans can help other Veterans with chronic pain management, and that they will be randomly assigned either to the Veteran peer coach group or to the group receiving a pain self-management class. Eligible patients must 1) have musculoskeletal pain in the low back, cervical spine, or extremities (hip, knee, or shoulder) for  $\geq 3$  months; 2) have at least moderate pain severity, defined by pain  $\geq 5$  on a 0 (no pain) to 10 (worst pain imaginable) scale; and 3) indicate willingness to engage in phone or in-person contact on a regular basis with another Veteran. We have identified approximately 26,000 unique outpatients who meet criteria 1 and 2. Patients will be excluded if the electronic medical record indicates a diagnosis of a psychotic disorder (e.g., ICD-9 codes 295-295.9 for schizophrenia), current substance dependence (e.g., ICD-9 codes 304-304.9), severe medical conditions precluding participation (e.g., NY Heart Association Class III or IV heart failure, ICD-9 codes 428-428.9), or if the eligibility screener given to prospective participants reveals active suicidal ideation, severe hearing or speech impairment, or pending surgery for a musculoskeletal condition (e.g., back surgery).

### **Control Arm**

Veterans will be randomized to either the peer coaching arm or a control group consisting of a 2-hour class in pain "basics" and pain self-management. In this class, topics listed in Part 1 (Self-Management Knowledge) of Table 1 will be reviewed (e.g., chronic pain basics, relaxation skills, activity pacing), and Veterans will be given a set of pamphlets related to pain self-management. [name] will lead the control group class; she has taught similar classes in other studies. Control participants will complete baseline assessments just prior to the class, to help encourage class attendance. (They receive compensation for assessments, see D3). We estimate offering one class per month during the study, with more offered as needed during heavier recruitment periods. To maximize attendance, some classes will be offered in the evening.

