### **Data Collection Protocol for Primary and Secondary Measures (Aims 1 and 2)**

Assessments will be given at baseline, 6 and 9 months. Participants (intervention and control) will receive \$30 per assessment. We will administer the same measures to peer coaches and Veterans, because research suggests peer coaches also benefit from peer interventions. Moreover, we want to determine whether the peers experience any negative effects related to their participation.

After obtaining informed consent, a research assistant will administer a baseline assessment to gather socio-demographic data, review the Veteran's history with an emphasis on previous and current pain treatments, and administer measures of primary and secondary outcomes. These assessments will take approximately 30 minutes each.

**Aim 1 (Primary Outcome): To compare 6- and 9-month effects of peer-supported chronic pain self-management versus controls on overall pain.** Overall pain will be measured with the Brief Pain Inventory (BPI) total score. The BPI was developed to assess the severity of pain and the impact of pain on daily functioning, and has been validated in primary care studies. The BPI is the average of two scores: pain intensity and pain interference. The pain intensity score is an average of 4 ratings of 0 (no pain) to 10 (pain as bad as you can imagine) for current, least, worst, and average pain in the past week. The BPI pain interference score averages seven ratings, 0 (does not interfere) to 10 (interferes completely), of interference with general activity, mood, walking ability, normal work, relations with other people, sleep, and enjoyment of life. The BPI total score will be used as the primary outcome measure because BPI total has been shown to be highly responsive to change in clinical trials. The BPI has been shown to have strong internal consistency in its original validation study (Cronbach's  $\alpha = 0.77$ ), the SCAMP study ( $\alpha = .83$ ), and IMPPRESS ( $\alpha = .88$ ); and the BPI assesses the two most important domains—severity and interference—recommended for pain studies.

**Aim 2 (Secondary Outcome Measures): To compare 6- and 9-month effects of peer-supported chronic pain self-management versus controls on self-efficacy, pain coping,**

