**Randomization.** Veterans will be randomly assigned to one of the two study arms using a table of random numbers generated by our statistician, [name]. To obtain the random treatment assignment for the 215 Veterans, five blocks of 43 Veterans will be used, and random treatment allocation will occur within each block to maintain the allocation ratio consistently across blocks. This block size is large enough to prevent investigators and research staff from guessing which treatment comes next in the sequence, while still allowing the allocation ratio to remain consistent.

**Data Analysis: Baseline Comparability.** Because of the size of this study, it is expected that randomization will produce treatment groups that are comparable and balanced. To test this assumption, we will tabulate baseline characteristics of participants and assess for potential imbalance in variables such as sociodemographics, depression, and anxiety across study arms. Additionally, descriptive statistics for baseline characteristics of peer coaches will be assessed (e.g., treatment history, including opioid use). Continuous variables will be assessed with graphical displays and summary statistics (means, standard deviation, range, etc.). Frequency distributions and percentages will be calculated for categorical data.

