**Data Analysis for Aim 1.** We will summarize total BPI score at each time point (baseline, 6, and 9 months) for both study arms. To compare the primary outcome of total BPI score at each time point relative to baseline between two treatment arms, we will use a linear mixed-effects model fit to all time points. This model will allow us to compare the change in BPI from baseline to 6 months (primary endpoint) between treatment groups, while accounting for the correlation of measurements from the same Veteran/peer coach and adjusting for confounding factors. Fixed effects in the model will include an indicator for treatment group, time (baseline, 6, and 9 months.), treatment group by time interaction, and covariates found to differ significantly between treatment and control arm. Random effects will include a random patient-specific intercept and a random effect for peer coach within the treatment arm only. Additionally, the variance may be allowed to differ between treatment and control arms. Because this is a randomized trial design we do not expect covariates to significantly differ between the two groups. However, if there are statistically significant differences, these covariates will be included in the model. The linear mixed model for subject  $i$  in therapy group  $j$  at time  $k$  is

$$y_{ijk} = \beta_{10} + b_i + x_{ijk}'\beta + \gamma_{11}t_{ij1} + \gamma_{12}t_{ij2} + (1 - I_{ijk})r_{ijk} + (\beta_{20} + b_i + \gamma_{21}t_{ij1} + \gamma_{22}t_{ij2} + u_j + e_{ijk})I_{ijk}$$

where  $I_{ijk}$  is an indicator if patient is assigned to the treatment group,  $x_{ijk}$  is a vector of fixed covariates,  $t_{ij1}$  is an indicator for the 6-month time point,  $t_{ij2}$  is the indicator for the 9-month time point,  $b_i \sim N(0, \varepsilon^2)$  are patient-specific intercepts,  $\mu_j \sim N(0, \sigma_j^2)$  is the random effect due to peer coach  $j$ ,  $e_{ijk} \sim N(0, \sigma_T^2)$  and  $r_{ijk} \sim N(0, \sigma_C^2)$  are the residual errors for each treatment group. All analyses will include checking of assumptions and model fit. Our statistical model, which accounts for nesting of Veterans within peer coaches, will allow us to calculate the intra-class

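### Control participants give their baseline pain score just before the control-only class, when they can infer their arm, and nothing places baseline before randomisation in either arm

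*Combined protocol and SAP*

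**What the plan says.** The Control Arm section of the combined protocol and SAP fixes when controls are assessed: "Control participants will complete baseline assessments just prior to the class, to help encourage class attendance". The same section defines the control condition as that 2-hour class and, on frequency, says "We estimate offering one class per month during the study".

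The inclusion/exclusion text under Recruitment of Veterans says candidates will be told that "they will be randomly assigned either to the Veteran peer coach group or to the group receiving a pain self-management class".

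The Data Collection Protocol gives the only general statement on baseline timing: "After obtaining informed consent, a research assistant will administer a baseline assessment". It does not mention randomisation.

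The Randomization paragraph says "Veterans will be randomly assigned to one of the two study arms using a table of random numbers". It describes five blocks of 43 but not whether assignment comes before or after baseline.

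Data Analysis for Aim 1 makes baseline part of the primary contrast: "This model will allow us to compare the change in BPI from baseline to 6 months (primary endpoint) between treatment groups". On the model terms it says "Fixed effects in the model will include an indicator for treatment group", along with time and their interaction. The treatment arm therefore has its own baseline mean.

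**The concern.** A baseline is protected by randomisation because it is measured before anyone knows the assignment. Here that protection is given up for controls. They have been allocated, they know what the two arms are, and they are about to sit the class that only controls attend. The BPI is entirely self-reported, so disappointment, relief or expectation about the assigned arm can colour the answers. For the coaching arm the order is simply not stated.

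Because the model estimates a separate baseline mean for each arm and tests the difference in change, any allocation-driven gap at baseline is subtracted from the 6-month gap. If controls over-report pain at baseline and this fades, they seem to improve more and coaching looks worse. If they under-report and this fades, coaching looks better. Adjusting for covariates that differ significantly between arms does not repair a shift in the baseline outcome itself. The pain screen of 5 or more comes before enrolment, but it is not the BPI, and the documents do not say the score is kept.

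There is a second consequence. A control Veteran who never attends a class may have no baseline at all. Missing baselines would then arise after allocation and in one arm only, which sits badly with the planned intent-to-treat analysis.

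**Working it through.** **Order of events.** Setting the sections side by side:

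| Step | Control arm | Coaching arm |
|---|---|---|
| Told what the two arms are | At recruitment | At recruitment |
| Baseline after consent | Yes (Data Collection Protocol) | Yes (Data Collection Protocol) |
| Baseline relative to assignment | After: they are already control participants, about to attend the control class | Not stated |

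That controls know their arm is an inference, since no section says when assignment is disclosed. No other reading fits the Control Arm and recruitment text together.

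**Possible size.** The plan has no figure of its own to reproduce here. Inputs from Sample Size Determination: 102 coaching and 80 control Veterans evaluable, two-sided alpha .05, target effect .4. Assumed, because the documents do not give them: the reporting shift, how much of it persists to 6 months, and the within-person correlation rho (.3 to .7). Also assumed: total SD 1, equal variances in the two arms, complete baseline and 6-month data, and .4 in single-time-point SD units.

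1. *Bias in the change contrast* = (control shift − coaching shift) × (1 − persistence).

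2. *Standard error.* The Aim 1 section says "Random effects will include a random patient-specific intercept and a random effect for peer coach within the treatment arm only". Neither effect has a time index in the model equation, so both cancel from the change. Then SE = √[2(1 − rho)(1/102 + 1/80)], where 1/102 + 1/80 = 0.0223:
   - rho .3: √(1.4 × 0.0223) = 0.177
   - rho .5: √(1.0 × 0.0223) = 0.149
   - rho .7: √(0.6 × 0.0223) = 0.116

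3. *Type I error* = P(|Z + bias/SE| > 1.96):

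| Bias (SD) | Share of .4 | rho .3 | rho .5 | rho .7 |
|---|---|---|---|---|
| 0.025 | 6% | 5.2% | 5.3% | 5.5% |
| 0.05 | 12.5% | 5.9% | 6.3% | 7.2% |
| 0.075 | 19% | 7.1% | 7.9% | 9.9% |
| 0.10 | 25% | 8.7% | 10.3% | 13.9% |
| 0.15 | 37.5% | 13.6% | 17.1% | 25.4% |

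4. *Persistence.* A net shift of 0.05, 0.10 or 0.15 SD that has gone by 6 months gives the rows with those values. If half persists, the rows are 0.025, 0.05 and 0.075. If all persists, the bias is zero.

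5. *Shift in the coaching arm too.* With a control shift of 0.10 SD, gone by 6 months, a coaching shift of 0.10, 0.05 or −0.05 SD gives net bias of 0, 0.05 or 0.15 SD.

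**Simulation check** (6,000 runs per case, 34 coaches × 3 against 80 controls, time-constant coach variance .3). The SD of the contrast was 0.175–0.178, 0.147–0.151 and 0.116–0.117 at rho .3, .5 and .7, matching the formula. At rho .5, a 0.10 SD control-only shift persisting 0, 50 or 100% gave bias of 0.099, 0.052 and 0.000. The coaching-arm shifts in step 5 gave 0.002, 0.048 and 0.150.

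**Sensitivity to clustering.** Sample Size Determination applies an intra-class correlation of .3 when powering the test of change. Using its design effect, 1 + (3 − 1) × .3 = 1.6, on the coaching arm gives SE = √[2(1 − rho)(1.6/102 + 1/80)] = 0.199, 0.168 and 0.130. Type I error is then 7.9–12.0% at a bias of 0.10 SD and 11.7–21.1% at 0.15 SD.

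**The case against.** The strongest case against has four parts.

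- **Coaching arm.** Nothing says that baseline follows allocation there, and the public text is incomplete, so the sequence may be set out in removed material. This stands as a limit: for coaching, the point is a request to state the order. It does not touch the control arm, where the text is explicit.
- **Harm is conditional.** Bias needs a reporting shift that differs between arms and fades by 6 months, and the documents support none of these. Controls still know their arm at 6 months, so a shift could well persist and do little or no harm. This also stands. But unmasked follow-up is inherent in comparing a coach with a class, while an unmasked baseline is avoidable. The plan also has no way to tell such a shift from chance imbalance or a treatment effect.
- **The figures depend on modelling choices.** Including coach clustering lowers the Type I figures, as shown. If .4 is in change-score SD units, a 0.10 SD bias is 21–32% of target, since 0.10/(.4 × √[2(1 − rho)]) = 0.21, 0.25 and 0.32 at rho .3, .5 and .7. The illustration moves, but the mechanism does not.
- **The timing is deliberate.** It is meant to get controls to the class, which is their whole intervention. That is a real cost of changing it. It is not a sufficient reason for attendance to decide when the primary outcome's baseline is measured.

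**Conclusion.** The concern holds. For controls, the plan takes the self-reported baseline of the primary outcome after allocation and at a point that reveals it. For coaching, the order is unstated. The bias is possible, of unknown size and direction. Under the assumptions above, a net shift of 0.05 to 0.15 SD that has gone by 6 months would amount to 12.5–37.5% of the target effect, with Type I error from about 6% to 25%. With half persisting, the range is about 5.2% to 10%. With full persistence, or equal shifts in both arms, there is no bias. The sequence for controls is certain from the text; the harm is not. This should be fixed because prevention is cheap, and confidence that it matters in practice is medium.

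**What to change.** State in the Data Collection Protocol and Randomization text that every Veteran completes the full baseline assessment after consent and before assignment is generated or disclosed, by the same route in both arms. Delete the Control Arm sentence that ties baseline to the class. State, for both arms, the date from which 6 and 9 months are counted.

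This reorders an existing 30-minute assessment with the same staff, measures and $30 payment, and leaves the sample size unchanged. It also removes the risk that controls who miss the class have no baseline. The costs are:

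- The baseline payment no longer draws controls to the class, so attendance may fall by an amount the documents do not let us estimate. The evening classes remain.
- Some controls may need one extra contact, unless baseline is done at the consent contact, which the stated sequence allows.
- With about one class a month, baseline may precede the class by some weeks, which is why the counting date needs stating.
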